The principal investigator is an attending anesthesiologist with extensive experience in clinical research.

Signatures

Principal Investigator

Principal Investigator
Signature

Principal Investigator
Name Printed

Date

The Principal Investigator signature is ONLY required if this is a new protocol, a 5 year update or a modification changing the Principal Investigator.

Department Chair

BY SIGNING THIS DOCUMENT THE DEPARTMENT CHAIR AGREES:

1. To work with the investigator and with the board as needed, to maintain compliance with this agreement.
2. That the Principal Investigator is qualified to perform this study.
3. That the protocol is scientifically relevant and sound.

Department Chair or Designee
Signature

Department Chair or Designee
Name Printed

Date

The person signing as the Department Chair cannot be the Principal Investigator or a sub-investigator on this protocol.
The Department Chair or Designee signature is ONLY required if this is a new protocol or a modification changing the Principal Investigator.

Brief Summary/Abstract

We have chosen to study the reconstructive spinal surgery patient population because we believe that the use of alvimopan in these patients at the University of Virginia will give the scientific community significant insight into the broader applicability of this drug into other surgical populations, the impact of this drug on the perception of pain (as opposed to simply the consumption of opioids), and its impact on total hospital charges, resource utilization, and functional outcomes.

Background

Provide the scientific background, rationale and relevance of this project.

Pain control following major spine surgery is difficult to achieve. Opiates are often necessary in high doses, and may be associated with significant side effects. Such side effects may include urinary retention, altered mental status, depressed respiratory drive, and constipation, and may lead to reduced nutritional intake in the postoperative period. Importantly, post-operative nutrition may impact the incidence of complications following spine surgery.¹

An emerging body of data suggests that intraoperative opiate use results in increased post-operative opiate requirements²⁻⁴ although this is controversial.⁵⁻⁷ Because of the side effects associated with opioid use, much effort has been devoted to the development of alternative and/or complementary analgesic regimens. Unfortunately, in early 2009 much of the promising data on alternative/complementary analgesic modalities was shown to have been fabricated. In all, twenty-one peer-reviewed papers in support of ketorolac, COX-2 inhibitors (celecoxib, rofecoxib, and valdecoxib), clonidine, verapamil, venlafaxine, pregabalin, and gabapentin were retracted. Thus, the goal of achieving improved perioperative pain control is as important, and distant, as ever

Alvimopan is a peripheral-acting opiate antagonist designed to decrease the gastrointestinal complications of perioperative systemic opioid administration. It has been studied in 11 randomized, controlled trials encompassing 4175 patients over the course of seven years. In all but one study, bowel recovery was improved following alvimopan administration, and in all but two, post-operative analgesia was reportedly unaffected

Despite existence of a large, growing body of literature supporting the use of alvimopan, further analysis is warranted for several reasons. First, and foremost, all eleven randomized trials of alvimopan were conducted using in patients undergoing intraabdominal surgery. While these patients universally suffer from post-operative ileus (because of proximity between the site of surgery to the GI tract), other patient populations (such as major spine surgery patients) also suffer from post-operative ileus

Second, the vast majority of data on alvimopan assesses effective analgesia by comparing morphine equivalents between groups (the implication being that if morphine equivalents are equal, no inhibition of analgesic effect has occurred). This methodology does not actually assess pain control or patient satisfaction

Third, several studies have shown an improvement in time to discharge or discharge order⁸⁻¹², without examining whether or not the difference in time to discharge translated into a reduction in hospital charges. Bell et al. pooled data from several alvimopan trials and estimated that mean hospital costs were reduced between \$879 and \$977 per patient, although this analysis was not based on the neurosurgical patient population.⁸

Lastly, the primary outcome in all eleven randomized, clinical trials is some variation of return of GI function. Patients who undergo reconstructive spinal procedures offer an additional clinical outcomes – functional status and postoperative satisfaction (as measured by the Oswestry Disability Index [ODI], the short form 12, and the short form 36 scores)

Hypothesis to be Tested

Primary Objective: examine the impact of alvimopan on time to first bowel movement in patients who undergo major spinal surgery

Primary Hypothesis: the perioperative use of alvimopan in major spine surgery reduces the time to first bowel movement

Secondary Objective: examine the impact of alvimopan on:

- overall hospital cost
- quality of recovery
- pain scores

Secondary Hypotheses: the perioperative use of alvimopan in major spine surgery

- 1) reduces overall hospital cost [even when taking into account the cost of the drug]
- 2) results in earlier resumption of full PO intake and consequently improved post-operative nutrition

Study Design: Biomedical

1. Will controls be used? Yes

► IF YES, explain the kind of controls to be used. placebo controlled study

7. What is the study design?

Randomized, Double-Blind, Placebo-Controlled Trial

8. Does the study involve a placebo? Yes

► IF YES, provide a justification for the use of a placebo

Compelling methodological reasons for use of placebo;
Participants are not deprived of interventions they would otherwise receive; *and*
Research intended to develop interventions that will benefit the host population.

Human Participants

1. How many subjects will sign a consent form under this UVA protocol? 60

2. Provide an estimated time line for the study. 100% enrolled in 2 years

Inclusion/Exclusion Criteria

INSTRUCTIONS:

The inclusion and exclusion criteria should be written in bullet format.

If this is a collection of only retrospective* specimens or data, the inclusion criteria must include a start and stop date for when specimens/ data will be collected.

The stop date must be prior to the version date of this protocol.

*Retrospective: all specimens are in a lab at the time this protocol is approved by the IRB. All data exists in medical records or records from previous studies at the time this protocol is approved by the IRB.

1. List the criteria for inclusion

1. Major spine surgery scheduled as part of clinical care
2. 18-80 years

2. List the criteria for exclusion

1. More than three doses of any opioid within one week of surgery
2. Pregnancy-
3. Prisoners
4. Unable to provide consent
5. Emergency surgery
6. Chronic kidney disease stage 5 (GFR < 15 ml/min)
7. Severe hepatic impairment
8. Recent myocardial infarction (within the last 3 months)
9. Allergy to any study related medications
10. Participation in another interventional study during the study period

3. List any restrictions on use of other drugs or treatments.

None

Statistical Considerations

a. Is stratification/randomization involved? Yes

► IF YES, describe the stratification/ randomization scheme.

- randomization will occur to either the alvimopan or placebo group after confirmation of eligibility on the day of surgery
- the randomization will be performed and the blind maintained by the Investigational Pharmacy

► IF YES, who will generate the randomization scheme?

UVA Investigational Drug Service (IDS)

2. What are the statistical considerations for the protocol?

For the purpose of the final analysis, the official clinical database will not be unblinded until medical/scientific review has been completed at the end of the entire study, protocol violators have been identified (if appropriate), and data has been declared complete.

[name] will perform the analysis for UVA

[name] will extract data from CDR. [name] works for the Department of Anesthesiology and extracts data as part of his routine job duties

Statistical Methods: For continuous variables, normality will be assessed using the Kolmogorov-Smirnov test. The Mann-Whitney U-test will be used to compare non-normally distributed data, and normally distributed data will be assessed by the Student t-test for equality of means. Categorical data will be analyzed using χ^2 or Fisher's exact test, if the count is < 5 in any cell. .

1. Time to event data (time to first bowel movement) will be analyzed using the rank-sum test.

2. visual analog scale , overall hospital charges , time to resumption of PO intake , functional outcomes QR-40 will be analyzed in the following ways:

- 11-point Numeric rating scale and QR-40 will be analyzed by way of a mixed model for repeated measures (MMRM).
- For hospital charges, either a t-test or Wilcoxon rank sum test (depending on the assessment of normality, as noted above).
- For time to resumption of PO intake we will assume no censoring and will use the rank sum test. Finally pain scores will be calculated and displayed using summary statistics empirically without comparison testing.

All tests will be 2-sided and we will consider a P value <0.05 to be statistically significant.

3. Provide a justification for the sample size used in this protocol.

In order to power this study, we evaluated the mean time to first bowel movement at our institution, which was 3.27 days ($\sigma = 1.10$)

Based on published data 519 women undergoing gynecological surgery, we predict that perioperative alvimopan will reduce the time to first bowel movement by 30%.¹³ Assuming that the placebo group will require 3.27 days to achieve a bowel movement, that alvimopan reduces time to first bowel movement by 30% (0.98 days) without changing the standard deviation ($\sigma = 1.10$), and setting α to 0.05, power analysis suggests that we will need to randomize 42 patients in order to have a 80% chance of not making a type II error. To factor for a 10-15% dropout rate, we would recruit 60 subjects for this study.

4. What is your plan for primary variable analysis?

Time to event data (time to first bowel movement) will be analyzed using the rank-sum test.

5. What is your plan for secondary variable analysis?

visual analog scale ,overall hospital charges , time to resumption of PO intake , functional outcomes QR40 8) will be analyzed in the following ways:

- 11-point Numeric rating scale and will be analyzed by way of a mixed model for repeated measures (MMRM).
- For hospital charges, either a t-test or Wilcoxon rank sum test (depending on the assessment of normality, as noted above).
- For time to resumption of PO intake we will assume no censoring and will use the rank sum test. Finally pain scores will be calculated and displayed using summary statistics empirically without comparison testing.

6. Have you been working with a statistician in designing this protocol? Yes

[name]

7. Will data from multiple sites be combined during analysis? No

Biomedical Research

1. List the procedures, in bullet form, that will be done for RESEARCH PURPOSES as stipulated in this protocol.

- Subjects will be consented
- Prior to study randomization, subjects will undergo a physical exam and review of medical history
- All women of child bearing potential will have a urine pregnancy test performed prior to administration of study drug pre-operatively
- Subjects will be randomized to either the alvimopan or placebo group
- Alvimopan or placebo administered orally pre-operatively
- Alvimopan or placebo administered orally or per NG twice daily post-operatively for up to seven days post-operatively, or until the time of discharge, whichever occurs first, to a maximum of 15 doses
- All intraoperative data recorded on the anesthesia record will be collected prospectively.
- BIS scores, when available, will be collected at the completion of surgery.
- Neuromonitoring data (ex. latency, amplitude, significant signal changes) will be collected at the completion of surgery.
- Postoperatively, visual analog scale (VAS) scores will be assessed daily at morning rounds.
- Additionally, nutritional intake and in hospital complications will be recorded, as will the patient's report of pain (on the 0-10 pain scale), time to first solid intake, time to first flatus and bowel movement (**primary outcome**), time to first ambulation, and consumption of all pain medications (intravenous and by mouth).
- ICU stay and hospital stay will be noted Initial post-op pain management orders will be entered by the Anesthesiologist
- to standardize opioid requirements, patients will initially be ordered hydromorphone as the intravenous opioid of choice (PCA and prn), and will only be changed (fentanyl) if specifically requested by the primary service.
- Patients will also be ordered oxycodone as the initial PO opioid of choice, and only changed to other medications (hydrocodone) if specifically requested by the primary service
- At the completion of hospitalization, QR40 will be used to assess the patients' pain and quality of life at discharge.

Total patient charges will be extracted from the University of Virginia's Clinical Data Repository.

2. Will you be using data/specimens in this study that were collected previously, with the use of a research consent form, from another research study? No

3. Will any of the procedures listed in item # 1 have the potential to identify an incidental finding? This includes ALL procedures, assessments and evaluations that are being done for RESEARCH PURPOSES that may or may not be considered investigational. No

4. Do any of the procedures listed above, under question # 1, utilize any imaging procedures for RESEARCH PURPOSES? No

5. Will you be using viable embryos? No

6. Will you be using embryonic stem cells? No

9. Are any aspects of the study kept secret from the participants? Yes

▶ IF YES, describe: the randomized study drug/ placebo is blinded

10. Is any deception used in the study? No

9. Will your study involve measures (C-SSRS/BID/SCID etc.) used to assess for depression and/or suicidality for research purposes? No

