APPENDIX: Support Source

- Describe what will be provided and by whom.

Merck will provide study drug and placebo

Merck will receive data prior to publication, however will not be taking on the liability of sponsor

- Do you confirm that you will obtain a contract/ material transfer agreement with the provider via the Medical Center Procurement office or Office of Sponsored Programs (OSP) [contact]?

Yes

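### Secondary hypothesis 1 concerns hospital cost net of alvimopan, but the planned analysis tests patient charges and has no step that counts the drug

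*Combined protocol and SAP*

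**What the plan says.** Under Hypothesis to be Tested, the secondary objective is overall hospital cost. The first secondary hypothesis goes further and says that alvimopan "reduces overall hospital cost [even when taking into account the cost of the drug".

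The analysis is given twice, in Statistical Considerations under item 2 (Statistical Methods) and item 5 (secondary variable analysis). In both places the variable is charges: "For hospital charges, either a t-test or Wilcoxon rank sum test (depending on the assessment of normality, as noted above". The procedures list under Biomedical Research names the data source: "Total patient charges will be extracted from the University of Virginia", from its Clinical Data Repository. The repository appendix ticks one generic financial category that covers either charges or costs.

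On supply, the Support Source appendix says "Merck will provide study drug and placebo". The design is double-blind, and "the randomization will be performed and the blind maintained by the Investigational Pharmacy". The Pharmacy appendix caps dosing at 15 doses and has missed doses documented in the medical record and the CRF.

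The only economic figure is in the Background. It cites an analysis that "pooled data from several alvimopan trials and estimated that mean hospital costs were reduced between" $879 and $977 per patient, in a population that was not neurosurgical.

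**The concern.** The hypothesis makes a claim about a net quantity: what the hospital spends once the drug is counted. The analysis plan has no term for the drug. There is no unit price, no step multiplying doses by price, no cost-to-charge conversion, and no statement of whether study drug or placebo appears in the extracted totals. The variable also changes name, from cost in the objective and hypothesis to charges in the abstract, the analysis sections and the procedures list.

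At stake is the interpretation of one of the two secondary hypotheses. If the charges comparison came out in favour of alvimopan, a report could present a saving after drug cost using figures that may leave that cost out. A reader of the protocol could not tell whether they did. The primary endpoint, the sample size and patient safety do not depend on this.

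**Working it through.** **The plan's own figure.** No design figure exists for cost or charges. The one computed figure is 42 patients for the primary endpoint. With a difference of 0.98 days, SD 1.10, two-sided alpha 0.05 and 80% power, the two-sample t-test needs 20.78, so 21 per arm and 42 in total. It reproduces, assuming equal allocation, which the protocol does not state. On the same assumption, the smallest difference in charges detectable with 80% power is 0.89 SD at 21 per arm and 0.74 SD at 30 per arm. The documents give no SD of charges, so the charges comparison has no stated power.

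**What the extracted charges could contain.** Let D be the between-arm difference in charges apart from study drug, k the mean doses given in the alvimopan arm and P the unit price. The hypothesis concerns D + kP.

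| How study drug is billed | Difference the planned test sees | Net of drug? |
|---|---|---|
| Neither product billed | D | No; omits kP |
| Both billed alike at b per dose | D + b × (difference in mean doses) | No |
| Alvimopan only, at b per dose | D + kb | Only if b is on the same basis as P |

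Company supply and blinding make the first two rows plausible. No section says which row applies, and in none of them does the plan define P.

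**Scale against the cited saving.** Doses = 1 pre-operative + 2 × post-operative days. Seven days give 15, matching the stated maximum. Three and five days (7 and 11 doses) are my assumptions, as is every dose being taken. The break-even price is saving / doses:

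- 15 doses: 879/15 = $58.60; 977/15 = $65.13
- 11 doses: 879/11 = $79.91; 977/11 = $88.82
- 7 doses: 879/7 = $125.57; 977/7 = $139.57

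At these prices, a drug cost missing from the charges would be as large as the whole cited saving. This shows scale only: the cited figure concerns cost in other patients, and the protocol does not say whether it is already net of drug.

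**Effect on the test, as illustration.** Suppose the true net difference is zero and an amount equal to d SDs of charges is left out of the alvimopan arm. The chance of declaring a saving is P(T > t0.975), with T noncentral t, df = 2n − 2 and noncentrality d × √(n/2).

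| d (assumed) | n = 30 per arm | n = 25 per arm (60 × 0.85 = 51 patients) |
|---|---|---|
| 0 | 2.5% | 2.5% |
| 0.05 | 3.8% | 3.7% |
| 0.10 | 5.7% | 5.3% |
| 0.20 | 11.5% | 10.3% |

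The rate doubles to 5% at d = 0.083 (n = 30) or 0.091 (n = 25).

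**Joining the two scales.** If the omitted amount were $879 to $977, d = 0.20 would require an SD of charges of 879/0.20 = $4,395 to 977/0.20 = $4,885. At 30 per arm, d = 0.083 would require 879/0.083 ≈ $10,590 to 977/0.083 ≈ $11,770. Larger SDs give smaller effects. The documents do not show where this trial falls.

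**The case against.** The best defence is that the harm rests on an unknown. The Support Source appendix says who provides the product, not how the hospital account treats it. If alvimopan is billed to the patients who receive it, total charges may already contain it and there may be no bias. This stands. A reader might infer that the planned comparison is tilted towards a saving; the documents do not establish that.

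A second defence is that the charges comparison does answer an aim the protocol states. The abstract and the benefit section speak of "its impact on total hospital charges, resource utilization, and functional outcomes", the Background describes the evidence gap in terms of charges, and the secondary objective is plain cost. The drug clause appears once, in brackets. This also stands in part. It would be too strong to say that the economic aim as a whole is unanswered, or that the clause is its whole purpose. But hypothesis 1 as written includes the clause, and the plan never acts on it.

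A third defence is that the repository request covers costs as well as charges, so the right data may be obtainable. That is so, and it makes repair easier. But no analysis of costs is planned, and cost data alone would not show how company-supplied drug is valued.

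Finally, the false-saving rates could be read as estimates for this trial. They are not: every d is assumed, and the effect on the p-value may be small.

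**Conclusion.** The point holds as a mismatch between hypothesis and analysis. The hypothesis is cost net of drug, the analysis is charges, and no step connects them. Confidence in that is high, because both analysis sections and the extraction step are legible and agree with each other. A net-of-drug conclusion is not supported by the analysis as written, however study drug is billed.

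Whether the estimate is biased, and by how much, cannot be determined from the documents. That would need the billing rule, a unit price and the SD of charges, and none is given. The tempting stronger statement, that the trial will overstate the saving or carry a false-saving rate near 11.5%, needs study drug to be absent from the charges and the omitted amount to be 0.20 SD. Neither is shown.

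The consequence is limited to one unpowered secondary hypothesis. It should be corrected, because the correction is cheap and the price has to be fixed before results are known.

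**What to change.** Before unblinding:

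- State whether the endpoint is cost or charges, and use that term in the objective, hypothesis, analysis and extraction sections.
- Fix a unit price for alvimopan on the same basis, its source, and a sensitivity range.
- Ask for an extract itemised enough to identify study-drug lines.

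After database lock and unblinding:

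- Remove any study-drug or placebo lines from the totals in both arms.
- For each alvimopan patient, add doses given, from the medical record and CRF, times the unit price.
- Report the mean difference with a 95% CI, with and without the drug and across the price range. A bootstrap interval would serve if charges are skewed; a rank-sum p-value alone does not estimate a mean saving.

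Because the lines are inspected only after unblinding, under a rule and price already fixed, the check does not threaten the blind and needs no new role for the drug service.

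If the drug will not be added, delete the bracketed clause and reword hypothesis 1 as hospital charges excluding study drug. That is one edit, but it gives up the net-of-drug claim.

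The full repair costs protocol wording, an itemised extract and one derived variable, with no new patient data. The downsides are that a price source must be chosen and defended, the conclusion may depend on it, and the result may be less favourable to alvimopan.

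### The primary endpoint is labelled time-to-event but is given a rank-sum test, with no rule for patients discharged or withdrawn before a first bowel movement

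*Combined protocol and SAP*

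**What the plan says.** Under Statistical Considerations, the Statistical Methods (item 1) and the plan for primary variable analysis (item 4) say the same thing: "Time to event data (time to first bowel movement) will be analyzed using the rank-sum test". Neither says how to score a patient whose first bowel movement is not observed.

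Censoring is mentioned only for a secondary endpoint: "For time to resumption of PO intake we will assume no censoring and will use the rank sum test".

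In the Biomedical Research procedures (item 1), study drug is given "for up to seven days post-operatively, or until the time of discharge, whichever occurs first", so discharge before day seven is foreseen. Time to first bowel movement is one of the postoperative items recorded. The last patient assessment listed is the QR-40 at the end of the hospital stay, and no later contact is listed. The same list says that "ICU stay and hospital stay will be noted".

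On numbers, the sample size justification says "we will need to randomize 42 patients in order to have a 80% chance of not making a type II error" and then "To factor for a 10-15% dropout rate, we would recruit 60 subjects for this study". Human Participants (item 1) reads "How many subjects will sign a consent form under this UVA protocol? 60". The randomization scheme adds that "randomization will occur to either the alvimopan or placebo group after confirmation of eligibility on the day of surgery".

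The Data and Safety Monitoring Plan allows participation to be stopped (2.3) and says how withdrawals are reported to the IRB (2.5), but not how they are analysed.

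**The concern.** An ordinary rank-sum test cannot use a patient who has no time. Someone must decide whether to leave the patient out, count discharge as the event, give the worst rank, or censor. With no rule, that choice can be made after the data are seen, and the options can give different answers on the primary endpoint.

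What is at stake depends on discharge. If stays are similar in both arms, the unobserved patients are mainly slow placebo patients, and dropping them shrinks the contrast under test. If alvimopan patients go home earlier, more alvimopan patients are cut off. Dropping them, or treating discharge as the event, then makes alvimopan look faster than it is. The Background reports that several alvimopan studies found earlier discharge, so unequal stays cannot be ruled out.

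**Working it through.** **1. The plan's own figure.** Inputs from the sample size justification: placebo mean 3.27 d, reduction 0.98 d (alvimopan mean 0.7 × 3.27 = 2.29 d), SD 1.10, two-sided α 0.05, power 80%. The 1:1 allocation is assumed.
- Normal approximation: n per arm = 2 × (1.96 + 0.84)² × (1.10/0.98)² ≈ 19.8, so 20 per arm, 40 in total.
- Two-sided t-test: 20.78, so 21 per arm, **42 in total**, power 80.4%. The plan's figure reproduces.
- Rank-sum efficiency of 0.955 with normal data: 42/0.955 ≈ 44.

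All of this assumes an observed time for every analysed patient.

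**2. How late can a first bowel movement be?** Same inputs, assuming normality, P(T > t) = 1 − Φ((t − mean)/1.10):

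| Day | Placebo | Alvimopan |
|---|---|---|
| 4 | 1 − Φ(0.66) = 25% | 1 − Φ(1.55) = 6% |
| 5 | 1 − Φ(1.57) = 6% | 1 − Φ(2.46) = 1% |
| 6 | 1 − Φ(2.48) = 0.7% | 1 − Φ(3.37) = 0.04% |

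These are tails of the time distribution, not missing-data rates. Fewer than 0.1% of placebo patients exceed 7 days, so the issue is early discharge and withdrawal, not the seven-day dosing limit.

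**3. Simulation model.** Bowel-movement times are normal as above, truncated at 0 (true difference then 0.93 d). Stay is **assumed** lognormal with log-SD 0.35. There are 30 patients per arm and 10,000 trials per setting (Monte Carlo error up to about 1 point). With complete data, rank-sum power is 90%.

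**4. True effect, equal stays, stay independent of bowel recovery.** Power by rule:

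| Median stay | Unobserved, placebo/alvimopan | Left out | Discharge as event | Worst rank | Gehan-Wilcoxon |
|---|---|---|---|---|---|
| 4 d | 32/14% | 70% | 81% | 84% | 87% |
| 5 d | 17/6% | 81% | 87% | 87% | 89% |
| 6 d | 9/3% | 86% | 89% | 89% | 90% |
| 7 d | 4/1% | 88% | 90% | 90% | 90% |

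The cost of leaving patients out is 87 − 70 = 17 points at 4 d, 89 − 81 = 8 at 5 d and 90 − 86 = 4 at 6 d. A repeat with 2,500 trials gave 89 − 74 = 15 at 4 d and 90 − 83 = 7 at 5 d.

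Sensitivity of this result:
- If slow recoverers stay longer (correlation 0.5-0.7), the loss is 13-16 points at 4 d, 2-5 at 5 d and 0-2 at 6 d.
- With 26 per arm, left out against Gehan-Wilcoxon is 64 v 82% (4 d), 75 v 85% (5 d) and 80 v 84% (6 d).
- With 21 per arm it is 55 v 73%, 66 v 76% and 71 v 76%.
- If bowel-movement times are themselves lognormal, the loss shrinks: 93 v 97% at 30 per arm with 35/16% unobserved (stay SD here assumed 1.5 d).

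**5. True effect, alvimopan stay one day shorter (assumed).** The unobserved shares become nearly equal, and so does the power (correlation 0, 3,000 trials):

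| Stay, placebo v alvimopan | Unobserved | Left out | Gehan-Wilcoxon |
|---|---|---|---|
| 6 v 5 d | 9/6% | 90.4% | 90.6% |
| 5 v 4 d | 17/14% | 89.4% | 89.0% |
| 4 v 3 d | 31/30% | 88.7% | 85.7% |

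A repeat at 5 v 4 d gave about 91% against 89%.

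**6. No bowel effect, alvimopan stay one day shorter.** At 5 v 4 d, correlation 0-0.7, false claims *for* alvimopan (nominal 2.5%) are about 5-9% when patients are left out, 5-11% with discharge as event, under 1% with worst rank and 1-3% with Gehan-Wilcoxon. Total type I error with worst rank is 10-11%, nearly all of it against alvimopan. At 6 v 5 d, total type I error is 5-6% under every rule.

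**The case against.** **The size cannot be read from the documents, and the plan never says such patients would be left out.** Both are true. Leaving out is one possible handling, used here as a comparator. Even then, power at 30 per arm with equal 5-day stays is 81%, above the 80% target. The case therefore rests on the missing rule, not on the 4-day figures.

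**The power loss depends on equal stays.** This also stands. Earlier discharge together with a real bowel effect is arguably the likelier course, because the Background reports better bowel recovery in all but one trial. Step 5 shows no material loss there. Part of the reason is that shorter alvimopan stays push the left-out comparison towards alvimopan. The same push produces the false claims in step 6.

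**Naming Gehan-Wilcoxon is a preference.** Partly so. With equal stays of 5 days or more, any stated rule recovers most of the power, and a log-rank test would also keep these patients. The merit of Gehan-Wilcoxon is that it equals the planned test when every time is observed.

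A reader might also infer three things that the documents do not support:
- *That the 10-15% dropout is the unobserved share.* The 60 are those who sign consent, and randomisation follows on the day of surgery, so some dropout may come before randomisation.
- *That 42 is wrong.* It reproduces exactly, and 60 exceeds 42/0.85 ≈ 50.
- *That worst rank and discharge-as-event bracket the true answer.* Each applies one rule to both arms, and bounds would need opposite extremes. With a true effect and equal stays, the complete-data statistic fell outside the interval between them in 58%, 40% and 22% of simulated trials at 4, 5 and 6 days.

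**Conclusion.** The concern holds as a missing rule on the primary endpoint, paired with a test that cannot use unobserved times. It should be fixed; confidence is medium because the size is unknown. Every power and error figure rests on an assumed lognormal stay, and most on 30 patients per arm.

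On those assumptions, a material power loss needs short, similar stays. It largely disappears if alvimopan both works and shortens stay, and it is small at 6 days or more. Inflated false claims for alvimopan need a shorter alvimopan stay without a bowel effect, which is the less likely case. It would be too strong to say that the planned analysis is underpowered or biased: the documents do not show that any patient will go home before a first bowel movement.

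**What to change.** In Statistical Methods item 1 and in item 4, make the primary test a rank test that handles censoring, on all randomised patients. Censor those without an observed bowel movement at discharge or last observation. Gehan-Wilcoxon with permutation variance is the closest match to the plan; log-rank is acceptable. Name one in advance.

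Also:
- state the time origin and the end of observation;
- record the last-observation date for withdrawn patients;
- report Kaplan-Meier medians with 95% confidence intervals, and the number unobserved, by arm;
- because the test assumes discharge is unrelated to bowel recovery, prespecify rank-sum results with worst rank and with discharge as the event as sensitivity analyses, not as bounds. Only the named primary test decides.

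**Cost.** Wording in two places and one date per withdrawn patient. Hospital stay is already recorded, and no extra patients or visits are needed.

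**Downside.** With very short, unequal stays (4 v 3 d, no effect), Gehan-Wilcoxon type I error is about 5-10%, with the excess against alvimopan.

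**Optional.** Recording the date of a first bowel movement after discharge would remove the assumption (about 90% power and 5% type I error with complete times at 30 per arm), at the price of one contact for those patients.
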